Animal models provide direct evidence of this pathophysiological effect. In healthy animals, splanchnic nerve stimulation shifts blood into the central compartment, increasing preload and cardiac output. In dogs with cardiac pacing induced systolic heart failure, splanchnic vascular capacitance was decreased (Ogilvie RI, circulation 1992). In these dogs, surgical transection of the splanchnic nerve, terminating sympathetic tone, results in decreased preload as

measured by systolic and diastolic filling pressures and increased compliance of the left ventricle (Figure A). In humans splanchnic nerve blocks are commonly used for pain control in patients with intractable visceral organ cancer pain. The nerve blocks are done temporarily using anesthetic agents or more commonly permanently using neurolytic agents. Interestingly, the most common "sideeffect" of this therapy includes transient orthostatic hypotension due an increase in splanchnic vascular storage capacity, which typically is prevented by aggressive pre-procedural hydration (Eisenberg E, Anesthesia and analgesia 1995).

А

В

[figure not shown]

Figure B: Pressure-volume recording in left ventricle in same animal. Blue curves are the baseline recordings and red indicate pressure-volume loops after nerve transection. Nerve transection caused flattening of the end-diastolic pressure-volume relationship indicating higher compliance. Unpublished pilot data.

In addition to the strong evidence supporting splanchnic nerve blockade as treatment of volume overload, it is possible it will also treat cardiorenal syndrome. The autonomic nervous system plays a critical role in the regulation of the kidney. Though this system is not fully understood, preclinical and clinical studies indicate the presence of a hepatorenal reflex that inhibits the renal function and causes fluid retention. This reflex has its origin in the portal vein and is stimulated by portal congestion. The splanchnic nerves represent the afferent and partially the efferent arm of the reflex arch. Inhibition of this reflex pathway in animals and a small human pilot study was shown to improve renal function and urine production.

4. Design & Procedures:

This study will be a prospective, uncontrolled clinical trial. The study will not be controlled as invasive monitoring of hemodynamics will be performed, allowing clear demonstration of a cause-effect relationship. Furthermore, the goal of the study is to demonstrate proof of concept.

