2. Bilateral splanchnic nerve block performed by an anesthesiologist (see images below) (CS). Following the right heart catheterization procedure the patient will be prone on the abdomen. Central venous access remains in place. Needle will be placed under fluoroscopic guidance in the posterior chest wall. Anesthetic solution (1% lidocaine with epinephrine) (1:200.000) will be injected (10-15 ml on each side). Patient will then be placed back on his/her back and central

hemodynamics are recorded again for the next 1-1.5 hours, approximately every 15 minutes. The central venous catheter will be removed after the hemodynamic monitoring is completed in the catheterization laboratory. Unless the primary team requested the catheter to remain in place and the patient is moved to the intensive care unit.

Following the block, the subject will repeat the positional change of a leg raise at 30, 60, and 90 minutes post-block to observe any changes in shortness of breath symptoms.

Additional measurements include:

- Orthostatic vitals will be obtained at the end of the hour while in the catheterization lab (CS).
- Dyspnea questionnaire (CS)
- If medically indicated a Swan Ganz catheter will be left in place. This would enable continuous monitoring of central hemodynamics for the next 24h (q4h) (SOC).

Follow up procedures:

Following right heart catheterization and lidocaine splanchnic nerve block the patient will be monitored on the floor/CCU for at least 48 hours following nerve block (SOC).

- Continuous recording of urine output for 24 hours (SOC). They will then be asked to void again 3 and 8 hours after the placement of the nerve block and 24 hours after nerve block (CS).
- Basic vitals (SOC) and orthostatic vitals (CS) within 24 hours after nerve block, and record heart rate variability using a non-invasive wrist monitor (CS).

- Repeat labs 12-24 hours after nerve block (next morning) [BUN (SOC), BMP (SOC) and pro-BNP (CS)
- Labs: Angiotensin 2, plasma metanephrines (if on inotropes), plasma catecholamines, vasopressin and urine sodium will be collected immediately before and after the procedure
- Dyspnea questionnaire at 12-24 hours after nerve block (CS) and again at 48 hours
- Six minute walk test (CS) within 24 hours after block and again at 48 hours
- Weight the next morning after nerve block (SOC) and at 48 hours.
- Echocardiogram within 1-2 hours after nerve block (CS)

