- Positional change of bending over to evaluate 'bendopnea' (shortness of breath symptoms with bending over).

Phone Call

Subjects will be contacted by study team six months (\pm 14 days) following their nerve block procedure. The purpose of this call will be to obtain mortality status and document the number of inpatient admissions since the procedure.

Blood samples processing:

Some blood samples collected before and after the nerve block (plasma metanephrines, plasma catecholamines, angiotensin II and arginine vasopressin) will be processed (centrifuged) and stored at -70 degrees Fahrenheit before sent out to an external lab. Storage duration may vary between weeks to months. Samples will be stored in a research freezer located on the 7th floor of Duke North (cath lab research freezer). As part of the study, we will send blood for study-related laboratory tests to the Mayo clinic and Inter Science Institute. These would include laboratory tests such as metanephrines, vasopressin, catecholamines, and angiotensin.

Safety endpoints:

- The duration of the anesthetic block is estimated for 1.5 hours. The subject will be monitored for up to 1.5 hours in the catheterization laboratory (acute safety). Chronic safety up to 48 hours post procedure. Hereby the patient will be observed clinically on the floor or CCU per standard clinical care routine. Further the subject's medical chart will be observed for 6 months following study enrollment to evaluate for recurrent admissions for heart failure.

Incidence of major side effects like:

- Pneumothorax, possibly requiring a chest tube
- Aortic puncture with retroperitoneal bleed or hematothorax
- Spinal cord trauma with possibly paralysis

Incidence of minor side effects like:

- Orthostatic hypotension
- Pain at puncture site and intercostal neuralgia

- Gastrointestinal dysmotility including diarrhea, constipation and abdominal cramping
- Bleeding at puncture site

Efficacy endpoints:

The following efficacy endpoints will be evaluated:

- Primary: Reduction in central venous pressure and/or pulmonary artery pressure (diastolic) and/or pulmonary capillary wedge pressure at 30-60 minutes after nerve block
- Secondary: Increase in cardiac output, improvement in echocardiographic parameters like ejection fraction (increase), central venous pressure (decrease), pulmonary artery systolic pressure (decrease), right ventricular diameter (decrease), left ventricular diameter (decrease)

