Descriptive statistics of continuous outcomes will include sample size, mean, median, standard deviation, minimum and maximum. For categorical outcomes, the number and percentage of subjects in each category will be presented. Statistical comparisons will be made using t-tests for continuous outcomes and chi square or Fisher's exact test (depending on overall event rates) for categorical outcomes. Paired t-tests will be used to compare changes from baseline to post-intervention. All statistical analyses will be performed using SAS for Windows (version 8.2 or higher) or other widely accepted statistical or graphical software. Patient data listings and tabular and graphical presentations of results will be provided. Unless otherwise specified, a two-sided 0.05 level of significance will be used to declare change in pre- and post-procedure variables different.

For power analysis, our primary endpoint is decreased in central venous pressure following nerve blockade. Based on preliminary animal experiments, we anticipate a reduction of CVP of 25%. For a sample size of 16, If the true difference in the experimental and control means is 25%, we will be able to reject the null hypothesis that the population means of the experimental and control groups are equal with probability (power) .90. The Type I error probability associated with this test of this null hypothesis is 0.05.

There is no direct measure of technical success following attempted block of the splanchnic nerves. The location of the splanchnic nerves is estimated biased on human anatomy dissections and established nerve block protocols used by the anesthesiology department. Procedural success to block the splanchnic nerves will be assumed in 70% of the cases based on the experience in splanchnic nerve blocks in patients with intractable cancer.

13. Data & Safety Monitoring:

Due to the experimental nature of this intervention, data will be recorded after each subject completes the intervention for signs of unintended negative effects. These include hypotension, worsening renal function, or clinical deterioration. Additionally, patient's electronic medical data will be clinically screened for any traumatic complications from the nerve block for the first 24 hours postprocedure.

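### Section 12 names no paired test for binary before/after outcomes: chi-square or Fisher, the only categorical tests given, assume independent groups

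*Combined protocol and SAP*

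**What the plan says.** Section 4 (Design & Procedures) sets out a single-group study: "This study will be a prospective, uncontrolled clinical trial".

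Section 12 (Data Analysis & Statistical Considerations) gives three relevant rules.
- **General comparisons:** t-tests for continuous outcomes and "chi square or Fisher's exact test (depending on overall event rates) for categorical outcomes".
- **Change from baseline:** "Paired t-tests will be used to compare changes from baseline to post-intervention".
- **Significance level:** "Unless otherwise specified, a two-sided 0.05 level of significance will be used to declare change in pre- and post-procedure variables different".

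No paired method for categorical data appears anywhere.

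Two symptom checks in Section 4 are made on the same patients before and after the block.
- **Leg raise:** done once before the block (Procedure, item 1). Afterwards, "the subject will repeat the positional change of a leg raise at 30, 60, and 90 minutes post-block" (Procedure, item 2).
- **Bendopnea:** "shortness of breath symptoms with bending over", listed under both the pre-procedure tests and the follow-up procedures.

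The only independent groups described are the two heart failure types in Section 5, 10 patients each. No objective compares them.

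**The concern.** A statistician holding a yes/no symptom result from before and after the block finds only chi-square or Fisher in the plan. Both tests take the two rows of the table as separate samples. With 20 patients they would treat 20 before and 20 after results as 40 people. They use only the marginal counts and ignore how many patients improved and how many worsened, which is where the evidence of change lies.

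At stake are the p-values for these symptom checks. Real improvement may be reported as non-significant or, less often, chance change as significant. An unnamed test also leaves room to choose one after seeing the data.

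**Working it through.** **The plan's own figure.** The only computed figure is power 0.90 for the fall in central venous pressure, "For a sample size of 16". It cannot be reproduced because no SD is given; a paired t-test reaches 0.90 only if the SD of the change is about 28.8 percentage points (25/0.868). It concerns a continuous endpoint, and this point does not touch it. No power is stated for any categorical outcome.

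**Inputs.** n=20 (Section 5 target), n=16 (Section 12 power statement) and two-sided alpha 0.05 (Section 12). The documents give no symptom rates or within-patient correlation (phi), so every proportion and phi below is an assumption.

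**Step 1: type I error.** Suppose a proportion p is symptomatic both times. The variance of the before/after difference in proportions is 2p(1-p)(1-phi)/n. The unpaired test uses 2p(1-p)/n. In large samples its 1.96 cut-off therefore acts as 1.96/sqrt(1-phi):
- phi=0.5: 1.96/0.707 = 2.77, two-sided level about 0.006.
- phi=-0.3: 1.96/1.140 = 1.72, level about 0.086.

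Exact enumeration of the paired 2x2 table at n=20, p=50%:

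| phi | Chi-square | Fisher | Exact McNemar | Mid-p McNemar |
|---|---|---|---|---|
| 0.5 | 0.005 | 0.002 | 0.009 | 0.026 |
| 0 | 0.043 | 0.020 | 0.023 | 0.042 |
| -0.3 | 0.073 | 0.040 | 0.025 | 0.044 |

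The unpaired levels drift with phi and chi-square can pass 0.05. Both McNemar versions stay below 0.05 here, although the exact one is itself conservative at this sample size.

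**Step 2: one table worked through.** Take n=20, with 12 symptomatic before and 5 after. The pooled expected counts are 17/2 = 8.5 and 23/2 = 11.5.
- Uncorrected chi-square: (12-8.5)^2 x (2/8.5 + 2/11.5) = 12.25 x 0.409 = 5.01, p=0.025.
- Continuity-corrected chi-square: p=0.055. Fisher: p=0.054.
- Exact McNemar, if 7 improved and 0 worsened: 2 x 0.5^7 = 0.016.
- Exact McNemar, if 9 improved and 2 worsened (same margins): 2 x (1+11+55)/2^11 = 134/2048 = 0.065.

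The unpaired p-values are identical in the last two cases, although the evidence of change differs.

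**Step 3: power.** Assume 60% symptomatic before, 60% of them resolving and 5% of the rest worsening. Then P(improve) = 0.60 x 0.60 = 0.36, P(worsen) = 0.40 x 0.05 = 0.02 and the post-block rate is 0.60 - 0.36 + 0.02 = 0.26. The implied phi is (0.24 - 0.60 x 0.26)/sqrt(0.60 x 0.40 x 0.26 x 0.74) = 0.084/0.215 = 0.39. Exact enumeration gives:

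| n | Fisher | Chi-square | Exact McNemar |
|---|---|---|---|
| 20 | 0.45 | 0.60 | 0.65 |
| 16 | 0.31 | 0.51 | 0.45 |

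If 15% of the rest worsen instead of 5%, at n=20 chi-square has 0.46 and exact McNemar 0.43.

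In a second scenario (80% falling to 50%, phi=0.3), mid-p McNemar has more power than chi-square at both sizes: 0.612 against 0.528 at n=20, and 0.468 against 0.438 at n=16.

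**The case against.** **The plan does not tie these tests to before/after data.** Section 12 separates general comparisons from change from baseline, and chi-square or Fisher is correct for HFpEF versus HFrEF. A reader might infer that the plan explicitly prescribes an unpaired test for symptom change; no sentence does so. What remains is that the categorical rule is unrestricted, the change-from-baseline rule is a t-test that does not suit a yes/no answer, and the significance level is stated for pre/post change. The plan is at best silent on paired binary data and at worst directs the wrong test.

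**Few outcomes are affected.** The listed symptom endpoint is the dyspnea questionnaire (7-point Likert and visual analogue scale) and the walk test, with no responder definition. Orthostatic data are numeric vital signs, and orthostatic hypotension is listed as an incidence of side effects. It becomes a paired binary outcome only if it is dichotomised both before and after. Leg raise and bendopnea are not in the endpoint list and are not defined as yes/no. This stands and limits the point to secondary or exploratory observations.

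**The power loss is not general.** A reader might infer from the Fisher results alone that the named tests always cost power. The plan also allows chi-square, and with expected counts of 8.5 and 11.5 that would be the usual choice. Uncorrected, it leads to the same conclusion as exact McNemar in the example with 7 improved and 0 worsened, and at n=16 it has more power. This stands too. It does not rescue the unpaired tests, since their error rate still depends on an unknown correlation.

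**Conclusion.** The point holds as a minor one. For binary before/after observations in the same patients, the only categorical tests in Section 12 rest on an independence assumption that fails. They are too conservative when a patient's two answers are positively correlated, and chi-square is too liberal when the correlation is negative. Loss of power is possible, clearest with Fisher (0.20 below exact McNemar in the n=20 scenario), but uncorrected chi-square is close to exact McNemar or above it. These sizes rest on assumed rates and correlations. The independence failure does not: it follows from the single-group design.

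The primary haemodynamic endpoint, the sample size and the stated power are unaffected.

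**What to change.** Add to Section 12 that:
- binary pre/post outcomes will be compared with McNemar's test, either exact or mid-p and chosen in advance, and reported with the paired difference in proportions and its 95% CI;
- for leg raise, the comparison uses one named post-block time out of 30, 60 and 90 minutes, with the other times described only;
- chi-square or Fisher is used only between separate groups (HFpEF versus HFrEF).

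If bendopnea, leg-raise dyspnea or orthostatic hypotension is to be tested in this way, state its yes/no definition for both time points.

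The cost is a few sentences, with no new data and no change to procedures. The one trade-off is that exact McNemar can have less power than uncorrected chi-square at n=16. Mid-p recovers much of that and kept its level below 0.05 in the cases checked.

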*Plasma Metanephrines will be performed only if subject is on inotropes **Phone call will capture mortality status and number of subject admissions to the hospital since procedure

Following enrollment into the study the subject will undergo the following tests/measurements. A majority of the clinical testing occurs as part of routine clinical care and will be marked as SOC (like in the above table). Tests required only for the purpose of the study are marked with CS.

Pre-procedure: Following information will be collected from the patient charts that will

- be done as standard of care (SOC). Study specific tests/recordings are also listed below:
- If the subject is female and childbearing potential and has not had a pregnancy test since the arrival to the hospital, a blood pregnancy test will be done (CS). If positive the subject will be excluded from the study.
- Subjects will have strict measurement of urine output (SOC). Additionally, subjects will be asked to void 3 hours prior to their procedure. They will be asked to void again immediately prior to the start of the procedure. A urine sample will be sent to the laboratory to check for the sodium concentration (CS). Subjects requiring a foley catheter will have measurements taken at comparable time intervals (SOC).
- Recorded vitals including weight, BP, HR, RR, SPO2 on the day before procedure and within 1h before procedure (SOC) and record heart rate variability using a non-invasive wrist monitor for 5 minutes (CS).
- Orthostatic vitals (5 minutes supine, 1+5 minutes sitting and 1+5 minutes standing) on the day before procedure and within 1h before procedure (CS)
- Labs: Basic metabolic panel (BMP) (SOC), brain natriuretic peptide (BNP) (SOC/CS), plasma angiotensin II (CS), plasma arginine vasopressin (CS), plasma catecholamines. Plasma metanephrines (CS) will be performed if subject is on inotropes. This will not require an extra lab draw. Total expected blood loss is <20ml.
- Dyspnea questionnaire using a 7-point Likert scale and Visual Analog Scale (CS)
- Six minute walk test (CS)
- Echocardiogram during the admission and no longer than 5 days prior to study (SOC). If no up-to-date echocardiogram is present, a study related Echocardiogram will be obtained (CS).
- If the patient is on diuretics medications the scheduling of the medication will be adjusted to minimize interference with the study intervention.

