 - Reduction in pro brain natriuretic peptide (pro-BNP)
 - Increase in UOP (output measured in ml/hour) and renal function (BUN and creatinine) in the hours following the procedure. Follow up for 48hours
 - Symptomatic improvement like a decrease in dyspnea (dyspnea questionnaire) and 6-minute walk test

5. Selection of Subjects:

Subjects will be recruited from Duke University Medical Center. All potential study subjects are admitted for ADHF and are treated as inpatient on the regular floor or in the intensive care unit.

The study will enroll subjects who meet the criteria as detailed below. Potentially eligible patients will be consented and entered into a screening process, which will include a chart review and physical examination. The primary enrollment target is up to 20 subjects (10 HF with preserved ejection fraction and 10 HF with reduced ejection fraction).

Inclusion criteria:

- Age 18-90
- Established diagnosis of HFpEF or HFrEF
- Admitted to DUMC for decompensated HF (NYHA stage 3-4, Class C-D), including patients on inotropic medication
- Symptomatic with dyspnea with clinical, radiographic or echocardiographic signs of fluid overload
- Planned for elective diagnostic right (+/- left) heart catheterization
- On a stable HF drug regimen prior to admission
- Anticipated hospital stay of at least 2 nights following catheterization procedure

- Preferably "diuretic resistant". Urine output <50ml/hour in the 24 hours preceding enrollment into the study.

Exclusion criteria:

Contraindicated medications:

- Anticoagulation at the time the procedure or in case of recent warfarin use an INR >1.4. Anticoagulation includes: warfarin, or novel oral anticoagulants like dabigatran, rivaroxaban, apixaban, endoxaban or full dose intravenous heparin products or bivalirudin and fondaparinux). Antiplatelet agents besides aspirin such as ticagrelor, prasugrel, Plavix are also considered to be a contraindication if used at time point of procedure.
- Immunosuppressive medications for solid organ transplant

HF medication regimen:

- Initiation of HF medications (in the 48 hours preceding the study) such as beta blockers, ACEI, ARB, aldosterone receptor blockers, calcium channel blockers of any type, central sympatholytics like clonidine, moxonidine,

- Recent acute MI or hemodynamic instability:

- Acute MI (STEMI or Type I NSTEMI) within 7 days?
- Evidence of progressive cardiogenic shock within 48 hours
- Repeat systolic blood pressure <90mmHg or >180mmHg

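### Section 12 lets every pre/post variable be declared different at two-sided 0.05, with no order, adjustment, key time point or exploratory label for the secondary endpoints

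*Combined protocol and SAP*

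**What the plan says.** Section 12 (Data Analysis & Statistical Considerations) names the test, "Paired t-tests will be used to compare changes from baseline to post-intervention", and the rule for reading it: "Unless otherwise specified, a two-sided 0.05 level of significance will be used to declare change in pre- and post-procedure variables different". The power paragraph in the same section concerns central venous pressure (CVP) only and adds "The Type I error probability associated with this test of this null hypothesis is 0.05". No section gives a multiplicity adjustment, a testing order, a designated time for any secondary endpoint, or a statement that secondary p-values are exploratory.

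The secondary endpoints are under Efficacy endpoints in Section 4. The list opens with "Secondary: Increase in cardiac output, improvement in echocardiographic parameters like ejection fraction (increase") and goes on to four more echocardiographic measures, introduced in a way that leaves the list open. It then gives pro-BNP, "Increase in UOP (output measured in ml/hour) and renal function (BUN and creatinine) in the hours following the procedure", dyspnea, and the 6-minute walk. The pre-procedure list in Section 4 shows that dyspnea is recorded on two scales: "Dyspnea questionnaire using a 7-point Likert scale and Visual Analog Scale (CS").

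Section 2 sets three objectives. Objective 2 is urine output and Objective 3 is creatinine clearance.

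**The concern.** The rule is worded as a declaration that a variable has changed, and it applies to whatever is measured before and after the block. Each such test has a 5% chance of a false declaration when nothing has changed, and the chance of at least one grows with the number of tests. With no order and no named time point, the analyst may report whichever variable and time crossed 0.05.

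Two features give this some weight. Objectives 2 and 3 are framed as questions the study will settle, yet they can be answered only through secondary variables that are measured several times. The study also has no control group, so no parallel arm is available against which to check a chance pre/post change.

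**Working it through.** **The plan's own figure.** The documents state no error rate for the set of secondary tests, so there is nothing to reproduce. The only stated type I error is 0.05 for the CVP test. The stated power of .90 with 16 subjects cannot be reproduced because no standard deviation is given, but this point does not depend on it.

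**Inputs from the documents.** Level 0.05, two-sided, per variable (Section 12). Paired t-test (Section 12). n = 16 (power paragraph, Section 12); enrolment is up to 20 (Section 5).

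**Counting variables (Section 4, Efficacy endpoints).** Cardiac output 1; ejection fraction, echo CVP, pulmonary artery systolic pressure, right and left ventricular diameter 5; pro-BNP 1; urine output 1; BUN 1; creatinine 1; dyspnea 1; walk test 1. Total 12, or 13 with Likert and VAS counted separately. The three primary pressures are not in this count.

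**Counting tests if every scheduled time is tested (an assumption).** Times come from the Table of Assessments and the follow-up list in Section 4.

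| Variable | Post-block times | Tests |
|---|---|---|
| Cardiac output | taken as one | 1 |
| Echo, 5 measures | 1–2 h | 5 |
| pro-BNP | within 2 h; 12–24 h | 2 |
| Urine output | 3, 8, 24, 48 h | 4 |
| BUN | next day; 48 h | 2 |
| Creatinine | next day; 48 h | 2 |
| Dyspnea, 2 scales | 3 to 4 times each | 6–8 |
| Walk test | within 24 h; 48 h | 2 |

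The sum is 24 to 26. It would be larger if cardiac output were tested at each 15-minute reading, or if weight, orthostatic vitals, heart rate variability, neurohormones or lung fluid were tested as well.

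**Independent tests, no true effect.** Chance of at least one declaration = 1 − 0.95^k.

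- k = 12: 1 − 0.95^12 = 0.460
- k = 13: 1 − 0.95^13 = 0.487
- k = 24: 0.708; k = 25: 0.723; k = 26: 0.737

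**Correlated tests.** The documents give no correlations, so these are assumed values. Simulated paired t-tests with n = 16 and an equal correlation between all changes (at least 20,000 runs) give:

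| Correlation | 13 tests | 25 tests |
|---|---|---|
| 0.3 | 0.43 | 0.62 |
| 0.5 | 0.35 | 0.49 |
| 0.7 | 0.25 | 0.34 |

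A second structure sets correlation 0.5 to 0.8 between repeat measures of one variable (24 to 26 tests, n = 20). It gives 0.55 to 0.70 when different variables correlate at 0 to 0.3, and 0.45 to 0.50 when they correlate at 0.5.

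**Beneficial direction only.** Each test then contributes 0.025.

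- 13 tests: 1 − 0.975^13 = 0.28 if independent; about 0.18 at correlation 0.5
- 25 tests: 1 − 0.975^25 = 0.47 if independent; about 0.25 at correlation 0.5

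**Expected number of false declarations, either direction, at any correlation.** 13 × 0.05 = 0.65; 25 × 0.05 = 1.25.

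**The case against.** The strongest defence is the nature of the study: single-centre, uncontrolled, up to 20 subjects, with proof of concept as its stated goal. Unadjusted secondary testing is common and tolerable at that stage if it is reported as such. The endpoints are labelled primary and secondary, and only CVP is powered. This stands as to severity. It does not remove the gap, because the proof-of-concept statement is given as a reason for having no control group, and the primary/secondary labels do not limit the rule in Section 12.

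Three stronger readings are tempting, and the documents do not support them.

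- A reader might infer that a false positive is more likely than not. That requires about 25 tests and low to moderate correlation. Twelve or 13 tests stay below one half even if independent, and 25 tests are at about one half or less once correlation reaches 0.5. Repeat measures of one variable, two dyspnea scales, and BUN with creatinine are unlikely to be independent.
- A reader might infer that about 25 tests are planned. The schedule says when data are collected. Section 12 compares baseline with post-intervention and does not say that each time is a separate test.
- A reader might infer that a chance secondary result ranks equally with the primary result. Sharing a significance level does not erase the labels.

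It is also fair to say that most secondary endpoints are stated with a direction, so the either-direction figures overstate the risk of a false claim of benefit. All the figures assume no effect on any variable, which is the worst case.

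**Conclusion.** The gap is real and minor. Section 12 permits a declaration of difference on any pre/post variable at 0.05, and nothing in the protocol narrows this for the secondary endpoints. The risk of at least one false declaration is well above 5% under every scenario examined. However, its size depends on two things the plan leaves open: how many time points are tested (13 tests against an assumed 24 to 26) and how strongly the changes correlate. The fair summary is a range from about one in four (13 tests, correlation 0.7) to about seven in ten (25 independent tests), and lower if only false claims of benefit count. No single headline percentage is warranted.

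Objective 3 adds a separate difficulty. It names creatinine clearance, while the endpoint list has BUN and creatinine, so no listed endpoint matches it as written.

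**What to change.** In Section 12, replace the sentence that sets the 0.05 rule with text to this effect:

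> The two-sided 0.05 level applies to the primary endpoint only. All secondary variables and time points will be reported as mean paired change with 95% confidence interval, labelled exploratory, without a declaration of difference.

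The definition of the primary endpoint must be settled separately, because Section 4 joins three pressures by and/or while the power paragraph uses CVP alone.

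If the sponsor wants a formal conclusion on Objectives 2 and 3, name one variable and one time point for each. Test them in fixed order after the primary, each at 0.05 and only if the preceding test succeeds. Objective 3 and the endpoint list must be reconciled first. This option is not needed for the basic fix.

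A Bonferroni adjustment would also control the error, but at 0.05/13 = 0.0038 or 0.05/25 = 0.0020 per test, which is severe with 16 subjects.

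The cost is fewer significance claims for secondary endpoints. No data, visits or sample size change.
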